3.8 Project Plan

The project aims to study the effect of two clinical treatments – **endovascular spasmolysis** and **elevation of cerebral perfusion pressure** – in patients suffering from severe vasospasm or local flow disturbances after acute SAH. The goal is to, with advanced supervision (multimodal monitoring), describe the treatments' effect size and duration on the brain's blood flow, as well as their possibility to reduce the risk of DCI after SAH.

The project is a prospective observational study conducted in two steps: an initial pilot study followed by a larger cohort study with two arms. Since the treatments are acute measures often initiated during on-call hours, the project has a pragmatic approach rather than a strict, inflexible protocol. A combination of clinically available methods will be used to continuously monitor the patients before, during, and up to 12-24 hours after initiated treatment.

Project Phases

- **Pilot trial (3–5 patients):** Aims to validate the study's feasibility, test logistics regarding data collection, and get a first idea of how long after treatment TCD data needs to be collected to see if/when blood flow returns to a baseline level.
- **Subsequent prospective cohort study spasmolysis** (goal 45-50 patients, 120-150 measurement occasions). Aims to collect data from a larger patient group based on experiences from the pilot study.
- **Subsequent prospective cohort study pressure elevation** (goal 100-110 patients where the spasmolysis group is expected to be included as a subgroup).

Feasibility With the current frequency of spasmolysis at Karolinska University Hospital, and considering TCD is not anatomically possible on all patients, we estimate being able to include approx. 10-12 patients annually to the spasmolysis analysis. Each patient may undergo approximately 1–5 treatments. For the pressure elevation cohort, approx. 25 patients/year are expected to undergo pressure elevation after aSAH at the department, most with some form of invasive intracranial monitoring. Both study arms assume that patients can be included and that data can be collected even at inconvenient hours, made possible by good coverage of research-active physicians and research nurses.

3.9 Patient Selection Criteria

Inclusion Criteria

- Adult individuals, 18 years or older
- Ongoing neurocritical care after subarachnoid hemorrhage
- Source of bleeding secured surgically or endovascularly
- Suspicion of developing or established severe cerebral vasospasm

Exclusion Criteria

- Expected survival less than 5 days, according to clinician's assessment.
- Not possible to perform TCD (too dense temporal bone, unclear or unstable TCD signal)
- Pregnancy

3.10 Case Report Form – CRF

eCRF is established with pseudonymized data on a platform approved by the Region and Karolinska Institutet, REDCap, an encrypted database with authentication and two-step verification. Patient key is stored in a local safe with a code within the operation's research premises where access is pass-card protected in two steps.

- Baseline variables including age, sex, comorbidities, and medications. Time of hemorrhage, clinical condition at admission according to GCS and injury grading according to Hunt & Hess, Modified Fisher, WFNS, Vasograde, and other relevant SAH-related variables collected in the existing quality database for SAH at Karolinska University Hospital.
- Baseline variables including cardiopulmonary data including biomarkers such as troponin and NT-proBNP, ECG & echocardiography for assessment of left and right ventricular function.
- Daily ordinary laboratory analyses and patient-related data and findings in the intensive care Patient Data Monitoring System, such as, for example, drainage rate of CSF from ventricular drains, microdialysis values, blood gas analyses, end-tidal carbon dioxide, fluid balance, electrolyte levels.
- Physiological monitoring via the software ICM+, including intracranial pressure (ICP), brain oxygenation (PbtO₂), brain saturation (SbtO₂), estimated cerebral blood flow (eCBF), flow velocities at continuous TCD, central temperature (brain and bladder), Pressure Reactivity Index (PRx), quantitative EEG (qEEG) including alpha/delta-ratio, ECG-analysis including heart-rate variability (HRV), pulse, intra-

arterial blood pressure, saturation (SaO₂), ventilator settings including fraction of oxygen.

- ICM+ annotation tools. Time-stamped changes in sedation, vasopressor or inotropic treatment, clinical or nursing intervention.
- Procedure-related information regarding endoluminal spasmolysis including time of decision for treatment, time of treatment, choice of drug, dose, potential stent treatment.
- Procedure-related information regarding endoluminal spasmolysis in the form of a questionnaire to the treating interventionist regarding treatment outcome including both subjective and objective parameters.
- Procedure-related information regarding pressure elevation and pressure reduction respectively, including time of decision for treatment, time of initiation of treatment, choice of drug for treatment, baseline value regarding cerebral perfusion pressure, target pressure and time duration to reach target pressure, causes and extent of deviation from target pressure.
- Procedure-related information and outcome at determination of cardiac output with capnodynamic method, cardiac output estimated through effective pulmonary blood flow (CO EPBF).
- Relevant drug treatment, including sedatives, beta-agonists, vasopressors, inotropic drugs, antihypertensive drugs, cardiodepressive drugs, diuretics, and electrolytes.
- Diagnostic basis for establishment and grading of cerebral vasospasm as well as associated phenomena such as cerebral salt wasting syndrome.
- Daily symptoms, clinical signs, neurological assessment.

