3.6 Specific Research Questions

1. What does the flow profile in the brain's vessels look like measured with continuous TCD **during** ongoing endoluminal spasmolysis in patients with severe cerebral vasospasm? Is the flow profile dose-dependent or independent? Is it possible to demonstrate a correlation between changed blood flow velocities and radiological outcome regarding macrovascular and microvascular spasm (visual estimation, mean transit time (MTT), etc.)?
2. **Secondary questions:** Are there correlations between radiologic treatment outcome and TCD flow velocities, intraparenchymal saturation and estimated cerebral blood flow (eCBF) or ischemic burden as determined by follow-up radiology, microdialysis or serial S100?
3. What does the flow profile in the brain's vessels look like measured with continuous TCD **before, during and after** endoluminal spasmolysis in patients with severe cerebral vasospasm? How long is the duration of effect regarding changed flow velocities in the brain's vessels after intervention? Is it possible to demonstrate an attenuation of the treatment effect with TCD to inform about the appropriate time for further treatment?
4. **Secondary questions:** Is there a correlation between duration of effect or effect attenuation measured with TCD with intraparenchymal saturation measurement, serial biomarkers like microdialysis or S100? Is there a correlation between duration of effect or effect attenuation measured with TCD with other neuromonitoring such as quantitative EEG (qEEG / Alpha/Delta-ratio)?
5. What does the temporal/dynamic flow profile in the brain's vessels look like, measured with continuous TCD and intraparenchymal oxygenation/saturation measurement **during and after** elevation of the cerebral perfusion pressure in patients with severe cerebral vasospasm?
6. **Secondary questions:** Is the effect of pressure elevation attenuated or improved over time measured with continuous TCD or intraparenchymal saturation? Is there a correlation between blood pressure level and flow profile measured with TCD and intraparenchymal saturation regarding the relationship to the brain's autoregulation window, determined with Pressure Reactivity Index (PRx)?

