3.7 Method

In this research project, we intend to increase the state of knowledge in severe cerebral vasospasm/DCI to better diagnose and monitor onset and progress, and to study possible outcome measures during and after treatment. We will study time series of blood flow velocities and pulsatility index in the brain's vessels with continuous and manual TCD respectively to establish effect outcome and duration of effect in connection to the established treatment methods: elevation of cerebral perfusion pressure and ES.

At pressure elevation, continuous TCD will be connected for measurement shortly before pressure elevation and measurement continues until the intended pressure level is reached and thereafter up to 12h after. If the patient has received intraparenchymal tissue saturation measurement or partial pressure measurement of oxygen, within the framework of clinical practice, these data will be included. The patient's cardiac output will be measured with a non-invasive capnodynamic method through the ventilator. A corresponding study design is also planned for planned pressure reduction.

At endoluminal spasmolysis, continuous TCD will be connected for measurement at the decision of treatment and continues during and up to 24h after treatment, to establish duration of effect regarding flow velocities according to the description in the questions above. Findings regarding blood flow velocities and duration of effect in cerebral vasospasm are primarily assessed as a proxy for the duration of effect regarding DCI. Additionally, we will link series of high and low-resolution information before, during, and after treatment with pressure elevation and endoluminal spasmolysis respectively, when such monitoring is established in the patient.

We intend to seek correlation in time series from continuous TCD with outcome measures with other invasive and non-invasive modalities (see above), and infarction extent on CT and infarction extent, blood flow, transit times on MRI-perfusion, possibly 4D-MR. In this way, we can enable a differentiation between duration of effect on flow velocities in vasospasm measured with TCD and possible duration of effect regarding ischemic burden, i.e., DCI. Overall, the project provides conditions to further describe the treatment modalities pressure elevation and endoluminal spasmolysis respectively and can contribute to a better understanding regarding their therapeutic potential and guide better and individualized treatment.

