
Primary Measurement Method:

- **Transcranial Doppler (TCD):** Measurement of blood flow velocities and derived variables in the brain's vessels. Continuous, robotized TCD is the first choice, intermittent manual TCD is the second choice. This is the mandatory measurement for all patients.

Secondary Measurement Methods (Multimodal Monitoring):

- **Neurological Monitoring:**
 - Frequent clinical neurological examinations (in awake patients)
- **Neuromonitoring data:** Available, already established invasive and non-invasive neuromonitoring data. This includes:
 - Quantitative EEG (including A/D ratio), Pupillometry, ICP, CPP, PRx, Cerebral microdialysis, Cerebral partial pressure of oxygen or local saturation, Local blood flow (rCBF).
- **Physiological monitoring data:**
 - MAP, Cardiac output with capnographic method, HRV, ECG.
- **Imaging:**
 - Angiographic data and intervention protocols (dose, location), Interventionist's subjective assessment of effect, Follow-up MRI- or CT-angiography.
- **Biomarkers (on clinical indication):**
 - **Brain injury markers:** S100b and GFAP in plasma. **Cardiac stress markers** (specifically during pressure elevation): Troponin and pro-BNP.

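### The treating interventionist rates the effect of spasmolysis while TCD is running, with no masking and no record of whether TCD was seen, so the visual or subjective part of the velocity-radiology correlation in questions 1-2 may be inflated

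*Protocol*

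**What the plan says.** Question 1 in Protocol section 3.6 asks whether the study can show a "correlation between changed blood flow velocities and radiological outcome regarding macrovascular and microvascular spasm (visual estimation, mean transit time (MTT), etc". Question 2 continues: "Are there correlations between radiologic treatment outcome and TCD flow velocities, intraparenchymal saturation and estimated cerebral blood flow (eCBF". Neither question says who makes the visual estimation or which radiological measure carries the correlation.

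Two other places describe how the effect of spasmolysis is rated. The imaging list in section 3.7 includes the interventionist's "subjective assessment of effect", next to angiographic data and follow-up angiography. Section 3.10 collects procedure information "in the form of a questionnaire to the treating interventionist regarding treatment outcome including both subjective and objective parameters".

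On timing, section 3.7 states that "continuous TCD will be connected for measurement at the decision of treatment and continues during and up to 24h after treatment". Section 3.10 time-stamps changes in sedation, vasoactive drugs and nursing interventions, but gives no completion time for the questionnaire. The protocol mentions no masking to TCD and no independent reader.

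Section 3.7 also plans to relate TCD to measures that do not come from the operator: "infarction extent on CT and infarction extent, blood flow, transit times on MRI-perfusion, possibly 4D-MR".

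**The concern.** A correlation between two measurements is informative about their agreement only if one was not used to form the other. Here one variable, the visual or subjective rating, may be supplied by the person who performed the procedure, while the other variable is being recorded in the same session. If the operator sees velocities fall and then scores the result as good, part of the rating is the TCD change itself.

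The agreement in question is not settled beforehand. The Background (section 2) says that no mean-velocity threshold has been shown to diagnose clinically significant angiographic vasospasm accurately, and it criticises current practice for letting subjective impressions steer treatment. Section 3.5 expects the results to inform later randomised trials. A TCD-angiography association produced partly by the rating process could therefore be carried forward as evidence that TCD tracks the effect of spasmolysis.

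The gap also has to be closed at data collection. Whether the rater had seen TCD cannot be reconstructed later if it was never recorded.

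**Working it through.** **What the text establishes**

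| Element | Protocol | Status |
|---|---|---|
| Velocity change is correlated with radiological outcome, including visual estimation | 3.6, questions 1-2 | stated |
| Operator supplies a partly subjective rating of effect | 3.7 imaging list; 3.10 | stated |
| TCD is recorded during the procedure | 3.7 | stated |
| Operator's rating is the visual estimation of question 1 | none | inference; no other rater is named |
| Operator sees the TCD trace | none | neither stated nor excluded |
| Rating is masked, ordered or time-stamped relative to TCD | none | not provided for |

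**The plan's own figure.** There is none for this correlation. The one calculated figure, 42 per treatment method in section 3.5, concerns mean velocity change. It reproduces with SD 20 cm/s, difference 5% of 200 = 10 cm/s, two-sided alpha 0.05 and power 90%: (20 × (1.960 + 1.282) / 10)² = 42.03. It serves below only as a convenient n.

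**Illustration on assumed weights.** Let X be an uninfluenced reading of the angiographic change and T the TCD change, both standardised, with true correlation r. Let the recorded rating be (1−w)X + wT. Then

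observed correlation = ((1−w)r + w) / √((1−w)² + w² + 2w(1−w)r).

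- r = 0, w = 0.1: 0.1/√0.82 = 0.11
- r = 0, w = 0.2: 0.2/√0.68 = 0.24
- r = 0, w = 0.3: 0.3/√0.58 = 0.39
- r = 0.3, w = 0.1: 0.37/√0.874 = 0.40
- r = 0.3, w = 0.2: 0.44/√0.776 = 0.50
- r = 0.3, w = 0.3: 0.51/√0.706 = 0.61
- w = 0: the observed correlation equals r, with no inflation.

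**False-positive rate when r = 0.** Take n = 42, one rating per patient, and Fisher's z with standard error 1/√39. The chance of a two-sided 5% rejection is 5% at w = 0, about 11% at w = 0.1, 34% at w = 0.2 and 74% at w = 0.3.

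**Rater bias unrelated to TCD.** Replace T in the rating by a standardised belief that is independent of both X and T. The observed correlation becomes (1−w)r / √((1−w)² + w²). For r = 0.3 this gives 0.27/√0.82 = 0.30, 0.24/√0.68 = 0.29 and 0.21/√0.58 = 0.28 at w = 0.1, 0.2 and 0.3. A constant shift toward favourable scores leaves a correlation unchanged. Inflation therefore needs the TCD reading to enter the rating.

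**The case against.** A reader might infer that the two variables are not independent and that the correlation will be inflated. The documents do not support that. No section says the interventionist watches the TCD, let alone that it shapes the score, and section 3.10 lists TCD velocities and the questionnaire as separate items. It is also an inference that the operator's score is the visual estimation in question 1, since section 3.7 lists angiographic data apart from the subjective assessment. These objections stand, and they limit the point to a conditional one.

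A reader might also count the operator's interest in a good result as a source of inflation. The last calculation shows otherwise: without TCD influence, such bias leaves the correlation unchanged or slightly weakens it.

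Nor do questions 3 and 4 rest on this rating. They concern the time course and duration of the TCD effect and its relation to saturation, biomarkers and EEG.

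Two further objections stand in part. First, the choice of measure for the correlation could be left to an analysis plan, and MTT and other imaging are already foreseen. But the order of rating and TCD viewing, and a record of exposure, cannot be supplied at the analysis stage. Second, the study is declared hypothesis-generating, and its primary analysis (section 3.12) is effect size and duration. This lowers the consequence without removing it.

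**Conclusion.** The point holds conditionally. As written, the only named rating of the effect of spasmolysis is unmasked to a TCD recording made at the same time, and exposure to that recording is not documented. Any velocity-radiology correlation that uses this rating could not be told apart from one created by the rater having seen the velocities.

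The size cannot be derived from the documents. The range of 0.11 to 0.39 for a true correlation of 0 rests entirely on assumed weights of 0.1 to 0.3, and the text equally permits a weight of 0. Only the visual or subjective component is exposed; MTT, perfusion transit times, infarct extent and follow-up angiography do not depend on the operator's score. This is a worthwhile, inexpensive improvement to data collection and does not undermine the study's primary aims.

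**What to change.** **Section 3.10.** Have the interventionist complete and time-stamp the questionnaire at the end of the procedure, before viewing the study TCD trend. Add one item recording whether TCD values were seen during the procedure. This restricts only the order of form-filling; clinical use of TCD stays as it is.

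**Section 3.6, questions 1-2.** State that the main velocity-radiology correlation uses quantitative imaging already planned: MTT, perfusion transit times, follow-up angiography, and objective angiographic items where they are recorded. Objective items on the questionnaire come from the same operator, so the ordering rule should cover the whole form. Report the subjective rating descriptively, with a sensitivity result limited to ratings made without sight of TCD. New vessel-diameter measurements are not required, because the protocol does not show that diameters are collected.

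**Cost.** One questionnaire item, an ordering rule and two wording changes, with no effect on sample size. There are two downsides. Where TCD was used clinically during the procedure, that rating drops out of the sensitivity result. Quantitative imaging will also not exist for every procedure: section 3.1 expects usually two to three perfusion examinations per care period, while section 3.8 expects about one to five treatments per patient. The main correlation will therefore rest on fewer occasions than there are procedures.

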3.11 Follow-up

Extended Glasgow Outcome Scale (GOSE) questionnaire and/or assessment at 3, 6, and 12 months respectively. When applicable; date of death.

3.12 Planned Analyses

Data will be presented descriptively as time series and by Granger causality analysis. Primary analysis will focus on describing the treatments' effect size and duration of effect. The association between treatment effect and ischemic burden (DCI) as well as relations to other collected parameters related to flow, metabolism, and injury will be evaluated. Extended analysis is expected to include dimensionality reduction of data with PCA and cluster methods, tree regressions, and other AI methods to identify composite patterns. Each patient will constitute their own cross-over control (comparisons are made before spasm, during spasm, and after treatment).

4 Ethical Considerations

Ethical application has been approved by the Swedish Ethical Review Authority, diary number 2025-05434-01. Many research subjects are unable to apprehend information or contribute to consent before inclusion. Consent with the patient is sought before inclusion when possible. In cases where the patient's condition does not allow consent, consultation occurs with the next of kin. This normally occurs before inclusion if the situation allows but shall be carried out at the latest the following day. Information regarding consent to the study is discussed at a separate meeting in a private room.

We apply a an opt-out procedure, where patients who improve during the care period and are assessed to be able to apprehend information will be informed and asked about study participation retrospectively. Patients who cannot apprehend information in such a situation shall be assessed, if possible, at outcome follow-up and then given information and a request for participation. This conversation is held by a physician or research nurse. If the patient or relative opposes participation and wishes to withdraw from the study, the research subject is excluded. Already collected data is retained within the framework of the study, but no further data is then collected. Research data is handled and saved pseudonymized in a secure environment. Research data is presented at the group level without the possibility of identifying specific patients.

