3.1 Overall purpose and conditions

The overall purpose of the research project is to characterize and better understand the disease course and treatment effects, including measurable duration of effect and potential link to outcome in severe cerebral vasospasm after subarachnoid hemorrhage. All clinical decisions and all treatment in the study patients occur entirely within the framework of ordinary care and practice.

The patient group is usually very well-monitored. In addition to one or two ventricular drains, patients with a confirmed diagnosis of severe cerebral vasospasm often receive multiple catheters in the brain parenchyma's watershed areas, such as pressure monitors (with temperature measurement and monitors for partial pressure of oxygen or local saturation) and microdialysis catheters, often bilaterally.

In attempts to answer the research questions, we intend to apply the following measurement methods:

1. **Continuous Transcranial Doppler (TCD)** with Delica EMS 9D (CE-marked) (27).
2. **Capnodynamics**, a non-invasive capnodynamic method for determining cardiac output via the patient's ventilator, Maquet Servo-I. The method is based on a periodically altered breathing cycle in the ventilator and is CE-marked for the purpose, validated, and shows good agreement with the golden standard (28,29).

3. **Continuous EEG** with automated analysis (alpha power, alpha-variability, and alpha/delta-ratio). Automated detection algorithms and integration with other neuromonitoring appear promising (30).

Otherwise, diagnostics and monitoring will occur within the framework of the department's clinical routine, as will the application of intraparenchymal cerebral catheters. No extra catheters or invasive procedures will take place within the framework of the study. The catheters Bowman® and Luciole® (both CE-marked) have the conditions to provide information on local blood flow and perfusion. Usually, two to three, sometimes more, MRI perfusion or CT-perfusion examinations are performed during the care period, which also gives a picture of local blood flow and perfusion in affected areas.

Overall, the multimodal neuromonitoring is expanded and can provide us with new cerebral blood flow-related parameters and their relation to cardiac output. The project has the possibility to contribute to a better understanding of the condition's course and provide guidance for improved and individualized treatment of this patient group.

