7. What relative increase in cerebral perfusion pressure or what absolute cerebral perfusion pressures are necessary to optimize cerebral blood flow during pressure elevation in severe cerebral vasospasm, measured with continuous TCD and intraparenchymal saturation, microdialysis, and qEEG?
8. **Secondary questions:** Can threshold levels regarding pressure/flow markers be identified? Does pressure elevation correlate to other desirable or undesirable systemic effects, such as impact on cardiac output, measured with capnodynamic method? At what pressure levels can the benefit/risk ratio be considered optimal based on an overall assessment?
9. Can predictors be identified to provide guidance on individualized/optimal cerebral perfusion pressures or treatment strategies in severe cerebral vasospasm?
10. In the early stage of cerebral vasospasm, can continuous TCD describe trends regarding the acceleration of flow velocities?
11. Does the acceleration follow a linear course, and can a trend analysis be applied to guide when treatment such as pressure elevation or endoluminal spasmolysis should be considered/initiated?

12. **Secondary question:** If the acceleration trend is non-linear, are there associations between acceleration measured with continuous TCD and other physiological, pharmacological, nursing, or patient-related factors?
13. Are there correlations between dynamic flow profile in the brain's vessels, measured with continuous TCD and intraparenchymal oxygenation/saturation measurement after endoluminal spasmolysis and perfusion pressure elevation respectively?
14. Do other clinically applied diagnostic modalities such as serum biomarkers, data from invasive brain monitoring (microdialysis, cerebral autoregulation (PRx), cerebral saturation, rCBF) and/or non-invasive such as continuous quantitative EEG, quantitative pupillometry, near infrared spectroscopy (NIRS), as well as infarction development on CT scan and blood flow velocities and transit time on MRI (4D-MR) provide associations with continuous TCD?

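### Section 3.12 calls each patient a cross-over control, but the plan is an uncontrolled before-after comparison in which later-hour effect and duration are mixed with natural course

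*Protocol*

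**What the plan says.** Protocol section 3.12 makes effect size and duration of effect the focus of the primary analysis and describes the comparison so: "Each patient will constitute their own cross-over control (comparisons are made before spasm, during spasm, and after treatment".

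The rest of the protocol fixes what that comparison can be:

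- Section 3.1: "All clinical decisions and all treatment in the study patients occur entirely within the framework of ordinary care and practice". Section 3.8 calls the project a prospective observational study. Its two arms are two treatments with overlapping patients, not treated against untreated.
- Section 3.7, spasmolysis: "continuous TCD will be connected for measurement at the decision of treatment and continues during and up to 24h after treatment".
- Section 3.7, pressure elevation: recording starts shortly before elevation, and "measurement continues until the intended pressure level is reached and thereafter up to 12h after". A matching design is planned for pressure reduction.
- Section 3.6, question 3 asks about duration and attenuation after spasmolysis, "to inform about the appropriate time for further treatment". Question 6 asks: "Is the effect of pressure elevation attenuated or improved over time measured with continuous TCD or intraparenchymal saturation".
- Section 3.6, question 10 treats a changing velocity as something to be studied: "In the early stage of cerebral vasospasm, can continuous TCD describe trends regarding the acceleration of flow velocities".
- Section 3.5 declares the study hypothesis-generating and expects it to inform later randomised trials.

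**The concern.** In a cross-over, patients receive the conditions in more than one order, so that treatment can be separated from time. Here every patient passes through the same sequence, and the clinician decides when treatment starts. Hours since treatment and hours of disease progression advance together. The word *control* tells the reader that natural course has been dealt with, and it has not.

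The protocol itself gives reason to expect an underlying trend. The Background (section 2) places delayed cerebral ischemia at about days 4 to 14, and questions 10 to 12 ask about the acceleration of flow velocity. Section 3.12 does not connect that trend with the before-after comparison.

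At stake is the reading of the primary outputs over 12 to 24 hours. A velocity that climbs back could mean that the effect has worn off or that the spasm has progressed. A velocity that stays low could mean a lasting effect or spontaneous resolution. Drift alone can produce either answer to question 6. Duration is meant to inform when further treatment is considered, so the ambiguity would be carried forward.

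The first of the three periods is also not assured in every patient. Section 3.9 admits patients with established severe spasm, and continuous recording around a treatment starts at the treatment decision or shortly before pressure elevation.

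**Working it through.** **1. What the sample size implies.** Inputs from section 3.5: mean velocity 200 cm/s, SD 20 cm/s, effect about 5%, alpha 0.05, power 90%, 42 per treatment method.

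- Target effect: 0.05 × 200 = 10 cm/s.
- Single group, two-sided, normal approximation: n = (1.960 + 1.282)² × (20/10)² = 42.03, which reproduces 42.
- Two independent groups on the same inputs: 2 × 42.03 = 84.06, so 85 per group, which does not.

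The stated figure is thus a one-group calculation of change, with no term for a comparator. This agrees with reading 3.12 as a before-after comparison.

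**2. Drift against the target effect.** If untreated velocity moves by d cm/s per day, the change seen h hours after the reference reading contains d × h/24 that is not treatment. The protocol gives no d; the values below are assumptions. Each cell shows the shift in cm/s and its share of 10 cm/s.

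| Assumed d (cm/s/day) | 10 min | 12 h | 24 h (spasmolysis only) |
|---|---|---|---|
| 3 | 0.02 (0.2%) | 1.5 (15%) | 3 (30%) |
| 5 | 0.03 (0.3%) | 2.5 (25%) | 5 (50%) |
| 10 | 0.07 (0.7%) | 5.0 (50%) | 10 (100%) |

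The shift can go in either direction. It is negligible around the procedure and grows with time.

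**3. Duration, as an illustration.** Assume a 10 cm/s fall that decays with half-life H, and call the effect ended when velocity is first within a tolerance of the pre-treatment level: the first t with −10 × exp(−t ln2/H) + d × t/24 above minus the tolerance.

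| H | Tolerance | d = 0 | d = +3 | d = +10 | d = −3 |
|---|---|---|---|---|---|
| 4 h | 2 cm/s | 9.3 h | 7.2 h | 5.1 h | not within 24 h |
| 6 h | 2 cm/s | 13.9 h | 9.8 h | 6.5 h | not within 24 h |

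The direction is the same in both rows: upward drift shortens apparent duration and downward drift lengthens it. The amount is not robust. Changing H from 4 to 6 h moves the no-drift answer by 13.9 − 9.3 = 4.6 h, slightly more than the 9.3 − 5.1 = 4.2 h due to a drift of +10. With H = 4 h and a tolerance of 3 cm/s, the d = −3 case first crosses at about 10.1 h instead of not within 24 h. This table therefore shows that duration is sensitive to drift; it does not estimate the bias.

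**The case against.** The strongest reply is that the design is disclosed. The parenthesis in 3.12 says what is compared, 3.8 says observational, 3.1 says ordinary care, and 3.5 says hypothesis-generating. No random order, washout or causal estimate is claimed. That is fair and limits the severity. It does not justify the label, which claims a control the design lacks.

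The protocol also has features that help. Section 3.8 expects about 1 to 5 treatments per patient and 120 to 150 measurement occasions, so treatment starts at different disease times. Section 3.10 collects the time of hemorrhage and time-stamped changes in sedation, vasopressors and nursing. Pressure reduction gives an on-to-off contrast. These mitigate in part. Pressure reduction is itself clinically timed and does not cover spasmolysis, and 3.12 does not bring these features into the comparison.

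The model for handling trend may properly sit in an SAP that is not shown, so its absence is not criticised here. The label is the protocol's own wording.

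Three stronger readings are tempting and not supported:

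- A reader might take return to baseline as the primary definition of duration. Section 3.8 uses it only for the pilot of 3 to 5 patients, to learn "how long after treatment TCD data needs to be collected to see if/when blood flow returns to a baseline level".
- A reader might put a figure on regression to the mean. It is possible, but the protocol states no velocity trigger for treatment (3.5 refers to clinical assessment for spasmolysis) and no untreated correlation, so it cannot be sized.
- A reader might say that 3.8 claims a proven reduction in delayed cerebral ischemia. That goal is already hedged, and 3.12 speaks of association.

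**Conclusion.** The point holds as a minor to moderate one. Section 3.12 names a cross-over control, whereas the design is an uncontrolled within-patient before-after comparison in one fixed order. Later-hour effect size, duration of effect and the answer to question 6 are confounded with disease time. Immediate peri-procedural changes are not materially affected, so the documents do not support a conclusion that the study cannot show a treatment response.

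That treatment and disease time are confounded follows from the text alone. The size does not: the 15 to 50% at 12 h and 30 to 100% at 24 h rest on assumed drifts of 3 to 10 cm/s per day, and the duration figures rest further on an assumed half-life and tolerance. The protocol specifies no hypothesis test at those hours, so no false-positive rate should be read into this.

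**What to change.** 1. In 3.12, replace *cross-over control* with *within-patient before-after comparison*, and state that later-hour effect size and duration are confounded with disease time.
2. Add one sentence to 3.12: effect size and duration will be adjusted for day after bleeding (available from the time of hemorrhage in 3.10) and, where recorded, for the pre-treatment velocity trend. Duration will also be reported under a stated range of untreated drifts, informed by the early-stage continuous TCD of questions 10 to 12. Leave the model itself to the SAP.
3. Report planned pressure reduction as a separate on-to-off contrast, noting that it too is clinically timed.

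Aligning the wording of the delayed-ischemia goal in 3.8 with the association wording of 3.12 is optional.

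The cost is a few sentences and somewhat more analysis, using data already planned for collection. Intervals will be wider and conclusions more modest. Adjustment reduces the confounding without removing it: early-stage drift is not a full substitute for an untreated course, so the drift range remains partly an assumption.
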